2.4 Correlative Studies Background

In order to evaluate the pharmacodynamics of ERK inhibition with BVD-523 we will obtain tissue samples from patients prior to enrollment and after approximately 15 days on treatment. These biopsies will be assessed by western blotting, to look at levels of ERK targets including DUSP, cyclin D, and others, and RNA seq to evaluate gene expression analysis. The goal of this correlative work is to determine if BVD-523 is appropriately inhibiting downstream signaling through ERK. In addition this testing will allow us to look at mechanisms of resistance to ERK

inhibition and predictors of response. In addition tumor will be assessed for the presence or absence of GNAQ and GNA11 mutations allowing for correlation with outcome.

Our understanding of the genetics of uveal melanoma is limited. A better understanding of the genetic diversity of uveal melanoma would be valuable to guide therapy and combinations of therapy in the future. We plan to perform whole exome sequencing in collaboration with the Broad Institute to gain a better understanding of the drivers of uveal melanoma

PARTICIPANT SELECTION

In this phase II study up to 25 patients with metastatic uveal melanoma will be enrolled to evaluate the efficacy of BVD-523. In the first stage 13 patients will be enrolled at which time an initial evaluation for efficacy will be performed. If sufficient efficacy is seen, we will enroll an additional 12 patients for a total of 25.

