13.1 Study Design/Endpoints

I. Primary Objectives

- a. To evaluate the overall response rate in uveal melanoma to ERK inhibitor therapy.

II. Secondary Objectives

- a. To characterize the safety profile of ERK inhibitor therapy when administered to adult patients with unresectable or metastatic uveal melanoma
- b. To evaluate overall survival of patients with uveal melanoma treated with ERK inhibitor therapy.
- c. To evaluate the pharmacodynamics of ERK inhibition with a comparison of pre- and on-treatment biopsies.

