13.6 Analysis of Secondary Endpoints

Secondary endpoints for this study include the rate of disease control, time to tumor progression, duration of response, safety of BVD-523, overall survival and correlative studies looking at drug effect and association of response with GNAQ and GNA11 mutation.

Disease control rate. The proportion of patients with best response of CR, PR, or SD lasting at least 24 weeks will be presented with a 90% exact binomial confidence interval. For a sample of size 25, the confidence interval will be no wider than 0.35.

Overall survival. Overall survival (OS) is the time interval between the start of treatment and death from any cause. OS will be censored at the date of the last follow-up visit for patients who become lost to follow-up.

Time to tumor progression. Time to tumor progression (TTP) is the time interval between the dates of the start of trial treatment and first documentation of progressive disease. In the absence of documented progressive disease, follow-up will be censored at date of last disease assessment.

Duration of response. Duration of response (DoR) is defined among patients with objective response (confirmed CR or PR as best overall response) as the interval between dates of first documentation of objective response and first documentation of progressive disease. In the absence of documented progressive disease, follow-up will be censored at date of last disease assessment.

The time-to-event endpoints will each be summarized using the method of Kaplan-Meier. Point estimates for each endpoint will be presented with 90% confidence intervals derived using log(-log(endpoint)) methodology.

Safety and Tolerability. All adverse events recorded during the trial will be summarized. The incidence of events that are new or worsening from the time of first dose of treatment will be summarized according to system organ class and/or preferred term, severity (based on CTCAE grade), type of adverse event, and relation to study treatment. Deaths reportable as SAEs and non-fatal serious adverse events will be listed by patient and tabulated by primary system organ class, and type of adverse event.

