Association between GNAQ mutation and outcome. To explore the association between GNAQ mutation and clinical outcome, tumors will be classified according to whether or not there is GNAQ mutation and compared with therapeutic response. The relationship between GNAQ mutation and progression-free survival will be explored using the method of Kaplan-Meier. Time to disease progression will be calculated, stratified by GNAQ mutation status.

Association between changes in levels of GNAQ, GNA11 or ERK effectors and outcome. Changes

in GNAQ or GNA11 expression, or change in ERK targets, will be documented with immunohistochemistry of tumor. Biopsies and blood/serum samples will be collected pre-treatment and 12-16 days after first treatment. Pre-treatment levels will be considered as predictors of clinical efficacy; changes in expression between pre- and post-treatment samples will also be related with clinical outcome. Pre-treatment levels and percent changes will be summarized using descriptive statistics.

For the analysis of association between change in biomarkers levels and response, we anticipate that approximately 90% of patients will have tissue for analysis at pre-treatment and again at 12-16 days, resulting in a potential sample size of 23 patients with paired biopsies. For a response rate of 0.25, this would result in six patients with response and 17 non-responders. Comparisons of biomarker change measured on a continuous scale will be based on two-sided Wilcoxon rank-sum tests with a type-I error of 0.1. There will be at least 80% power to detect differences in biomarker change that are approximately 1.35 times the common standard deviation of the change.

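### The pharmacodynamic objective is analysed only by a descriptive percent change, with no interval or paired test; the one powered biomarker test asks a different question and is uninformative if the trial stops at stage 1

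*Combined protocol and SAP*

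**What the plan says.** Section 13.1 (II.c, repeating section 1.3) sets the objective: "To evaluate the pharmacodynamics of ERK inhibition with a comparison of pre- and on-treatment biopsies". Section 2.4 gives its purpose: "The goal of this correlative work is to determine if BVD-523 is appropriately inhibiting downstream signaling through ERK". The list of secondary endpoints that opens section 13.6 includes "correlative studies looking at drug effect and association of response with GNAQ and GNA11 mutation", so drug effect is named separately from association with mutation.

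Section 13.6 has no paragraph on drug effect. Biomarker change is handled in the paragraph on its association with outcome, where "changes in expression between pre- and post-treatment samples will also be related with clinical outcome". The within-patient change itself gets one sentence: "Pre-treatment levels and percent changes will be summarized using descriptive statistics". The power statement that follows concerns a two-sided rank-sum test at 0.10 comparing responders with non-responders. Its starting assumption is that "we anticipate that approximately 90% of patients will have tissue for analysis at pre-treatment and again at 12-16 days". The plan counts this as 23 pairs. If a quarter of those patients respond, it expects 6 responders against 17 others. The claim is at least 80% power for a difference of about 1.35 SD of the change.

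The same section commits to 90% confidence intervals for disease control rate and for the time-to-event endpoints.

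**The concern.** The objective concerns one population quantity: how far ERK targets move from before to during treatment. The test with stated power concerns another: whether that movement differs between responders and non-responders. A null result on the second says nothing about the first, because equal inhibition in every patient makes the groups alike.

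This matters most after a negative trial. If few patients respond, the biopsies should help to separate a drug that missed its target from one that reached it without benefit. As planned, the only evidence on that question would be a summary of percent changes in a small sample with no commitment to show its precision. Patients undergo an on-treatment biopsy largely for this purpose.

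**Working it through.** **Inputs.** Section 13.6: about 90% of patients with paired tissue, 23 pairs, 6 responders and 17 non-responders, two-sided alpha 0.10, difference 1.35 SD, power at least 80%. Section 13.2: stop after 13 patients with 0 or 1 response; stopping probability 0.86 at a 5% response rate. No marker SD is given, so effects are in SD units of the change.

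**1. The plan's own figures.** 0.90 × 25 = 22.5, taken as 23; 0.25 × 23 = 5.75, taken as 6, leaving 17. Power of the exact rank-sum test, 6 versus 17, difference 1.35 SD, normal data, 40,000 simulated trials: 0.823. The noncentral t calculation gives 0.865, or 0.851 with the Wilcoxon efficiency 3/π. The stated power is right.

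**2. What that test measures.** If every patient's marker changes by the same amount d, the expected group difference is d − d = 0, whatever the size of d.

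**3. The test at a stage 1 stop.** Paired tissue: 0.90 × 13 = 11.7, about 12 pairs (assuming the 90% also holds at stage 1).
- One responder: the most extreme ranking has probability 1/12 in each tail, so the smallest two-sided exact p is 2/12 = 0.167. With all 13 paired it is 2/13 = 0.154. Reaching 0.10 would need 2/n ≤ 0.10, that is at least 20 pairs.
- The normal approximation does not rescue it. With 1 versus 11, z = (11 − 5.5)/√(11 × 13/12) = 5.5/3.45 = 1.59, below 1.645.
- No responders: there is no second group.

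At a 5% response rate, P(0 responses) = 0.95^13 = 0.513 and P(1 response) = 13 × 0.05 × 0.95^12 = 0.351. The sum is 0.865, against the stated 0.86. At a 25% rate the stopping probability is 0.127.

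**4. What the same biopsies could support.** Test of the mean within-patient change against zero, two-sided 0.10, 80% power:

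| | 23 pairs | 12 pairs |
|---|---|---|
| Normal approximation, (1.645 + 0.842)/√n | 0.52 SD | 0.72 SD |
| Paired t | 0.54 SD | 0.77 SD |
| Exact signed-rank, simulated | 0.55 SD (power 0.802) | 0.80 SD (power 0.800) |
| Half-width of 90% interval for the mean, t(0.95, n−1)/√n | 0.36 SD | 0.52 SD |

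Simulations assume normally distributed changes.

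**The case against.** The best defence is that this is a secondary correlative objective in a trial of at most 25 patients, worded as an evaluation by comparison, which does not oblige anyone to test a hypothesis. Descriptive reporting can be acceptable there. Nor would a test against zero settle the purpose in section 2.4, which asks whether inhibition is appropriate: a small, inadequate fall could still exclude zero. The pairs are also imperfect. Sections 3.1.9 and 9.0 allow different organs, and archival tissue up to 6 months old, so some of the measured change may not be due to the drug. Testing every ERK target at 0.10 would raise multiplicity, since the marker list is open-ended.

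All of this stands. It is why the paired test should be supportive only, tied to one lead marker, and secondary to an estimate with an interval. It does not explain why the comparison that the objective names gets no interval when other secondary endpoints in the same section do.

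Some stronger readings are tempting but unsupported:
- A reader might infer that the plan has no within-patient estimate, or cannot say anything about ERK inhibition. The percent change is a within-patient measure, and its summary is not conditional on response or stage. A large uniform fall would be visible, including after a stage 1 stop.
- A reader might set 0.55 SD against 1.35 SD as lost efficiency. The first is a mean change against zero and the second a difference between groups, so they are different estimands.
- A reader might infer that the rank-sum test requires six responders. Six is a planning assumption at a 25% response rate. With 23 pairs and two responders the smallest exact p is 2/253 = 0.008.

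**Conclusion.** The point holds as a gap between objective and analysis; the plan's power calculation is correct. Within-patient change, the quantity that objective II.c is about, is to be described without a stated interval, paired test or lead marker. The only powered biomarker analysis answers whether change is associated with response. It becomes uninformative in exactly the outcome that the design makes likely for an inactive drug: a stage 1 stop, probability 0.865 at a 5% response rate.

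The collected pairs can do more: about 0.55 SD is detectable with 23 pairs and about 0.80 SD with 12. These figures rest on normal changes and on 90% paired tissue at stage 1, which the plan states only for the full sample. Without a marker SD they cannot be translated into a degree of ERK inhibition. The change is worth making before analysis because it costs little. The primary endpoint is unaffected.

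**What to change.** Add one paragraph to section 13.6 as the analysis of objective II.c:

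- **Population.** All patients with paired biopsies, regardless of response or stage.
- **Measure.** Within-patient log ratio of on-treatment to pre-treatment level, or the difference for scores that can be zero.
- **Lead marker.** One ERK marker named in advance; the others exploratory.
- **Estimate.** Hodges-Lehmann estimate with a 90% confidence interval, matching the level used for the other secondary endpoints.
- **Test.** Two-sided signed-rank test at 0.10, supportive only.
- **Precision.** State the detectable change, about 0.55 SD with 23 pairs and about 0.80 SD with 12, with the assumptions above.
- **Responder comparison.** Keep the rank-sum test as a separate exploratory question.

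Two inconsistencies bear on the paired measure and should be reconciled at the same time. The assay is western blotting and RNA sequencing in section 2.4 but immunohistochemistry in section 13.6. The on-treatment biopsy falls within days 12 to 18 in sections 5.2.3 and 10.1 but at 12 to 16 days in sections 9.0 and 13.6.

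The cost is a little more analysis work, with no new samples, visits or patients. The text should say that an interval excluding zero shows that some change occurred, not that inhibition was adequate.

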13.7 Reporting and Exclusions

All safety data will be summarized using descriptive statistics and presented in patient data listings. Information on study treatment will be summarized by dose and cumulative dose using descriptive statistics. Adverse event data will be presented in frequency tables (overall and by intensity) by body system. In tables showing the overall incidence of adverse events, patients who experienced the same event on more than one occasion will be counted only once in the calculation of the event frequency. The worst grade of an event will be reported for any patient.

Laboratory data will be summarized for each assessment time using descriptive statistics for patients with marked abnormalities during study treatment based on NCI-CTCAE Version 5.0 criteria. Vital signs and physical examinations will be summarized for each assessment time using descriptive statistics and reported in patient data listings.

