3.1 Eligibility Criteria

- 3.1.1 Participants must have histologically or cytologically confirmed stage IV uveal melanoma.
- 3.1.2 Participants must have measurable disease, defined as at least one lesion that can be accurately measured in at least one dimension (longest diameter to be recorded for non-nodal lesions and short axis for nodal lesions) as ≥ 20 mm with conventional techniques or as ≥ 10 mm with spiral CT scan, MRI, or calipers by clinical exam. See Section 11 for the evaluation of measurable disease.
- 3.1.3 Patients can have received any number of prior therapies for treatment of their uveal melanoma excluding prior treatment with an ERK inhibitor. Patients who have received prior MEK inhibition or other MAPK targeted agents will be allowed on study.
- 3.1.4 Age ≥ 18 years of age.
- 3.1.5 ECOG performance status ≤ 2 (Karnofsky $\geq 60\%$, see Appendix A)
- 3.1.6 Life expectancy of greater than 6 months
- 3.1.7 Participants must have normal organ and marrow function as defined below:
- leukocytes $\geq 3,000/\text{mcL}$
 - hemoglobin $\geq 9.0 \text{ g/dL}$
 - absolute neutrophil count $\geq 1,500/\text{mcL}$
 - platelets $\geq 100,000/\text{mcL}$
 - total bilirubin $\leq 1.5 \times$ institutional upper limit of normal
 - AST(SGOT)/ALT(SGPT) $\leq 2.5 \times$ institutional upper limit of normal, unless there is known liver involvement in which case $\leq 5.0 \times$ institutional upper limit of normal
 - creatinine within normal institutional limits

OR

- creatinine clearance ≥ 60 mL/min/1.73 m² for participants with creatinine levels above institutional normal.
- 3.1.8 Participants must have adequate cardiac function, e.g. left ventricular ejection fraction (LVEF) of >50% as assessed by multi-gated acquisition (MUGA) or ultrasound/echocardiography (ECHO); corrected QT interval (QTc) <470ms.
- 3.1.9 Presence of metastatic disease that would be amenable to the required biopsies. Ideally pre and post biopsies should be from the same lesion and otherwise from lesions in the same organ. If not possible, then biopsy of the lesions in different organs will be permitted. Archival tissue from a biopsy taken within 6 months prior to the first study treatment may be used in place of a pre-treatment biopsy at the discretion of the principal investigator.

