7.1 Definitions

7.1.1 Adverse Event (AE)

An adverse event (AE) is any untoward medical occurrence associated with the use of a drug in humans, whether or not considered drug related. An AE can be any unfavorable and unintended sign (including an abnormal laboratory finding), symptom or disease temporally associated with the use of a drug, without any judgment about causality.

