8.1 BVD-523

8.1.1 Description

When BVD-523 was characterized using *in vitro* screens against 66 receptors and ion channels no toxicologically significant interactions were identified. Additionally, BVD-523 was negative in bacterial mutation and *in vivo* micronucleus screening assays, so BVD-523 is not considered to have a significant genetic toxicology risk.

While BVD-523 modestly inhibits the hERG current (IC₅₀ 3.4 μM), no significant effects were seen in action potentials recorded from dog Purkinje fibers exposed to up to 10 μg/mL, and no significant cardiovascular findings were observed upon acute oral dosing of the compound at dose levels up to 50 mg/kg in dogs (C_{max} = 17.3 μM). Thus BVD-523 is considered to have a low potential to cause QT prolongation in patients, but, as stated, the study will monitor for signs of cardiovascular effects of BVD-523 in humans.

No significant cytochrome P450 (CYP) inhibition has been observed with the compound. *In vitro* studies suggest that the compound is metabolized primarily via oxidation by multiple CYPs, including 3A4, 2D6, and 1A2. Furthermore, no significant CYP induction was observed after up to 14 days drug treatment in rats, nor during *in vitro* studies with human hepatocytes. These data suggest a limited potential for drug-drug interactions.

BVD-523 HCl salt is orally available in multiple species (absolute bioavailability %F = 23% in dog to 100 % in monkey) when formulated as a simple suspension in 1% carboxymethylcellulose (CMC) and has a half-life of 2–4 hours across all species.

BVD-523 was administered to male and female Sprague-Dawley rats in several toxicology studies: a GLP study for up to 28 days at dose levels up to 50 mg/kg/day twice daily; for up to 14 days at dose levels up to 100 mg/kg twice daily; and for up to 5 days at dose levels up to 150 mg/kg/dose once daily. The incidence and severity of mineralization seen in these studies was dose-dependent and effects were observed in 1 or more tissues at toxic doses. In animals in which mineralization occurred after treatment with BVD-523, significantly increased serum phosphorus and modestly decreased serum calcium were seen; these effects were not observed in animals in which there was no mineralization. Therefore, the risk of tissue mineralization can be assessed by serum phosphorus and calcium monitoring. A

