13.7.1 Evaluation of Toxicity

All participants will be evaluable for toxicity from the time of their first treatment.

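### The only laboratory-specific summary is limited to patients with marked on-treatment abnormalities, so by-visit levels are strongly attenuated and shifts below the threshold can be missed

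*Combined protocol and SAP*

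**What the plan says.** Section 13.7 opens with a general rule: "All safety data will be summarized using descriptive statistics and presented in patient data listings". It then gives one sentence on laboratory results: "Laboratory data will be summarized for each assessment time using descriptive statistics for patients with marked abnormalities during study treatment". Marked is tied to CTCAE version 5.0 but not to a grade. The following sentence has no such restriction: "Vital signs and physical examinations will be summarized for each assessment time using descriptive statistics and reported in patient data listings".

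Three other places bear on the point:

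- Section 13.7.1 sets the safety population: "All participants will be evaluable for toxicity from the time of their first treatment".
- Section 7.1.1 allows an abnormal laboratory result to be an adverse event. Section 13.7 tabulates those events: "Adverse event data will be presented in frequency tables (overall and by intensity) by body system". Section 13.6 adds the incidence of events that begin or get worse after dosing starts, by CTCAE grade and relation to treatment.
- Section 8.1.1 gives laboratory results a specific role: "Therefore, the risk of tissue mineralization can be assessed by serum phosphorus and calcium monitoring".

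Chemistry, including phosphorus and calcium, is drawn at screening, on Day 1 of each cycle and at the end-of-treatment visit (sections 5.2 and 10.1).

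**The concern.** The laboratory sentence chooses its population by the outcome it then describes. A patient enters the table because a value became extreme on treatment, and everyone whose values stayed unremarkable is left out. Levels in the table are therefore high (or low) by construction, and the set of patients is known only once treatment has been observed. A moderate shift across all patients that carries few of them over the threshold would have little effect on the levels shown.

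Safety is a secondary objective of this trial. Section 3.1.7 also admits patients with raised AST/ALT, with a wider limit (5 times the upper limit of normal) where the liver is involved. Some patients may therefore meet a threshold partly because of disease already present at entry. A level shown without its change from baseline does not separate that from a drug effect.

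**Working it through.** The documents give no figure for the laboratory summaries, so there is none to reproduce. What follows shows the size of the selection effect under stated assumptions.

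**Inputs.** From the documents: single arm, at most 25 patients (section 1.1), and selection by an on-treatment abnormality (section 13.7). Assumed, not from the documents: a standard normal analyte, one visit, marked means above c = +2 SD, and a drug shift d of 0 or 0.5 SD in every patient.

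**Step 1: mean level among flagged patients.** The formula is d + φ(c − d) / [1 − Φ(c − d)].

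- No effect: φ(2) / [1 − Φ(2)] = 0.0540 / 0.0228 = 2.373 SD.
- Shift of 0.5 SD: 0.5 + φ(1.5) / [1 − Φ(1.5)] = 0.5 + 0.1295 / 0.0668 = 2.439 SD.
- Difference shown: 2.439 − 2.373 = 0.066 SD, for a true shift of 0.5 SD.

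**Step 2: expected number flagged.**

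- No effect: 25 × 0.0228 = 0.57.
- Shift of 0.5 SD: 25 × 0.0668 = 1.67.
- Chance that nobody is flagged: (1 − 0.0228)^25 = 56% and (1 − 0.0668)^25 = 18%.

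**Step 3: the all-patient alternative.** Mean change from baseline is 0 against 0.5 SD. The 90% half-width is t(0.95, 24) × SD of change / √25.

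- If the SD of change is 1 (baseline/on-treatment correlation 0.5): 1.711 / 5 = 0.342 SD.
- In general the SD of change is √[2(1 − ρ)]. At ρ = 0.8 the half-width is 0.632 × 0.342 = 0.22 SD. At ρ = 0.3 it is 1.183 × 0.342 = 0.40 SD.

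**Step 4: several visits.** A simulation of 400,000 patients per setting used one baseline and four on-treatment values, within-patient correlations of 0.3, 0.6 and 0.8, and cut-offs of 1.5 to 3 SD, with selection on any on-treatment value above the cut-off. The table gives correlation 0.6 and cut-off 2 SD. The last column is the range, over all settings, of the difference between a 1 SD shift and no effect.

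| Quantity | No effect | 0.5 SD shift | 1 SD shift | Range of difference, 1 SD vs none |
|---|---|---|---|---|
| By-visit mean, selected patients | 1.50 | 1.65 | 1.83 | 0.17 to 0.54 |
| Mean worst value, selected patients | 2.40 | 2.48 | 2.61 | 0.10 to 0.32 |
| Change from baseline, selected patients | 0.21 | 0.67 | 1.12 | 0.81 to 0.96 |
| Number flagged of 25 | 1.7 | 4.3 | 8.7 | – |
| By-visit mean, all patients | 0.00 | 0.50 | 1.00 | 1.00 |

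By-visit levels thus show about a third of a true 1 SD shift (1.83 − 1.50 = 0.33). With no drug effect, selected patients still show a rise from baseline of 0.21 SD (0.08 to 0.55 over the settings), which comes from the selection alone.

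**The case against.** Several objections have force.

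- **Other laboratory reporting exists.** The general rule in 13.7 plans listings of all safety data, and with 13 or 25 patients these can be read line by line. Graded abnormalities can reach the adverse event tables, where every treated participant is evaluable. A reader might infer that laboratory toxicity as a whole has no denominator. The documents do not support that. What remains is that a listing is not a summary, and a shift below the threshold need not produce an event.
- **The table would not look the same with and without an effect.** A reader might infer that it would. That holds approximately for by-visit levels and worst values only. The number flagged rises about three-fold in Step 2, and change from baseline still separates the cases in Step 4. The laboratory sentence commits to neither display, however.
- **The sentence may be loose wording** for all laboratory data plus the patients with marked abnormalities. The text does not settle this. The unrestricted sentence on vital signs beside it favours the literal reading.
- **Baseline may be visible.** Chemistry is drawn before dosing, so a summary at each assessment could include pre-dose values, and the adverse event tables count only new or worsening events. That eases the concern about patients with liver disease. It does not give a change from baseline in all treated patients.
- **The mineralization link is limited.** A reader might infer that the restricted table would hide the mineralization signal. Sections 7.2 and 8.1.1 report the phosphorus and calcium changes in affected animals, and say they were absent where there was no mineralization. That describes a signal in individuals, which monitoring and listings can pick up, rather than a modest shift in everyone. Phosphorus and calcium still deserve a proper table because the protocol relies on them.

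**Conclusion.** The point holds in a limited form. The one laboratory-specific summary in 13.7 selects on the outcome and sits badly with the safety population in 13.7.1. It also states neither an all-treated denominator nor change from baseline. Its by-visit levels are strongly attenuated: 0.066 SD shown for a true 0.5 SD shift in the one-visit illustration, and 0.17 to 0.54 SD shown for a true 1 SD shift over the simulated settings. These sizes rest on an assumed normal analyte, cut-off and correlation. The direction follows from the selection rule itself.

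The consequence is confined to descriptive safety reporting. No test, stopping rule or decision in sections 13.2 and 13.4 uses the laboratory tables. This is an improvement available at almost no cost, and not a defect in the design or the primary analysis.

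**What to change.** Replace the laboratory sentence in 13.7 with three commitments:

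1. Summarise each analyte, with phosphorus and calcium named, and its change from baseline at each visit for all treated patients with a value, showing N.
2. Tabulate baseline CTCAE grade against worst on-treatment grade, with all treated patients as the denominator.
3. Define marked as a stated CTCAE grade and keep those patients as a supplementary listing.

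The cost is one reworded sentence and a few standard tables. The chemistry is already collected at screening, on Day 1 of each cycle and at the end of treatment. Sample size, type I error and power do not change.
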